4.4 Dose Delays/Modifications

Symptoms of local toxicity will be monitored throughout treatment. Treatment will be delayed for up to 2 weeks (14 days) if grade 2 local toxicity (not considered DLT) develops during pre-induction, induction, or maintenance phases. In addition, BCG dose modifications will be managed according to standard of care procedures; specifically, in the case of a grade 2 local bladder toxicity, the dose should be delayed, and BCG may be re-challenged at half the dose (25mg) per the treating physician's discretion within 2 weeks (14 days) of the last administration. Local toxicities related to the treatment with BCG and/or pembrolizumab include bladder spasm, cystitis noninfective, hematuria, urinary frequency, urinary retention, urinary tract pain, urgency. In addition, for grade 2 bladder or urinary tract infection, treatment *may be delayed* up to 2 weeks at the discretion of the treating physician; for grade 3 bladder or urinary tract infection, antibiotics are allowed with a 2 week delay of treatment as long as the infection has been cleared symptomatically. Treatment may resume when the toxicity resolves or improves to grade 1. If toxicity does not resolve to Grade 0-1 within 2 weeks (14 days) after scheduled dose, trial treatment should be discontinued after consultation with the PI and DSMC.

The patients will be allowed to delay treatment during induction or maintenance by up to 2 weeks (14 days) due to scheduling difficulties. When BCG is delayed due to local bladder toxicities, pembrolizumab will be delayed as well. Doses of pembrolizumab will not be reduced due to toxicities. BCG doses may be reduced following standard of care as described above. If the patient needs to undergo a transurethral biopsy or resection during the study, there will be a delay of approximately 4 weeks (per PI discretion) until the next treatment of BCG or pembrolizumab to allow healing of biopsy/resection site.

In addition, pembrolizumab will be withheld for drug-related Grade 4 hematologic toxicities, non-hematological toxicity \geq Grade 3 including laboratory abnormalities, and severe or life-threatening AEs. Delay by up to 2 weeks (14 days) is permitted. Treatment may resume when the toxicity resolves or improves to grade 1. If toxicity does not resolve to Grade 0-1 within 2 weeks (14 days) after the scheduled dose

administration, trial treatment should be discontinued after consultation with the PI and DSMC. With PI and DSMC agreement, subjects with a laboratory adverse event still at Grade 2 after 2 weeks may continue treatment in the trial only if asymptomatic and controlled.

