4 TREATMENT PLAN

4.1 Overview

Treatment will be administered on an outpatient basis. Treatment will be divided into pre-induction, induction and maintenance therapy phases. Two weeks prior to induction, subjects will receive the first intravesical instillation of pembrolizumab (week -2). During induction therapy, patients will receive standard intravesical instillation with BCG once weekly for 6 weeks (total of 6 BCG instillations). Patients will also be treated with concomitant pembrolizumab, given intravesically every 2 weeks during the induction period (total of 3 pembrolizumab instillations; weeks 0, 2, and 4). The maintenance phase starts at week 7 and continues up to 1 year (last dose and cystoscopy at week 49). Intravesical BCG and intravesical pembrolizumab will be given every 2 weeks for the first 12 weeks of maintenance therapy (weeks 7, 9, 11, 13, 15, 17 for a total of 6 doses) and then every 4 weeks thereafter (weeks 21, 25, 29, 33, 37, 41, 45 and 49 for a total of 8 doses) until completion of treatment or early discontinuation for any reason.

Cystoscopies will be performed 8 weeks (approximately 2 months) from the end of the induction period (week 17) and will be repeated at 8-week intervals until week

NU Study Number: NU 15U06
Merck Study Number: 3475-265

49. If ambulatory cystoscopy reveals any abnormal finding requiring further investigation, BCG and/or pembrolizumab administration will be suspended until clinical investigation is completed. Tumor progression will be defined as positive transurethral resection and/or biopsy including tumor stage progression, muscle infiltration or metastasis. Should a bladder cancer progression be confirmed, the subject will be off treatment and off-study. Otherwise, subject will be able to resume study treatments approximately 4 weeks (per PI discretion) after any bladder biopsy to allow appropriate healing. NOTE: the PI will review and confirm when appropriate healing has occurred to allow resumption of treatment. Any patient who has a high-risk lesion resected on a follow-up cystoscopy must be removed from study treatment.

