4.2.1 BCG

BCG will be administered weekly during the Induction phase of treatment, followed by maintenance BCG (see duration of therapy; section 4.8). Every effort should be made to administer treatments on the same day each week, however a window of +/- 2 days is allowed to accommodate scheduling issues. BCG administration should begin at least 2 weeks after any prior cystoscopies or intravesical procedures to allow healing of bladder epithelium. Each BCG dose will consist of 50mg BCG (TICE® BCG) diluted in 50ml of sterile normal saline that will be injected into the bladder through sterile urethral catheterization. There will be no dose escalation planned for BCG, however the dose may be reduced based on toxicity criteria in section 4.4. After emptying the bladder, the BCG solution will be injected intravesically over 1 or 2 minutes and retained for 2 hours. Following the administration, patients will receive instructions to drink large amounts of fluids and monitor for symptoms that can develop and be related to the BCG instillation: dysuria, urgency, frequency, hematuria, persistent fever (temperature above 101°F for more than 2 days), chills, night sweats, malaise, arthralgia, cough, or skin rash.

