4.3 Dose Escalation Scheme

There will be no dose escalation for BCG (patients on all cohorts will receive the same dose). The table below summarizes the pembrolizumab dose levels; subjects will receive the same dose of pembrolizumab during pre-induction, induction and maintenance phases. No dose reductions are permitted for pembrolizumab. BCG may be reduced for toxicity as described in section 4.4. A standard “3+3” dose escalation design will be utilized. Initially, the study will enroll 3 subjects at the starting dose (level 1), after which enrollment will be temporarily suspended until all 3 patients complete the DLT evaluation period (defined as the 2 week pre-induction phase and the seven weeks of induction phase). Once all 3 subjects complete the DLT period and toxicity data has been reviewed by the Northwestern University Data Monitoring Committee, a decision will be made to proceed with escalation accordingly the rules below.

Table 4-2: Escalation Dose Levels			
Dose Level	Pembrolizumab	BCG	Number of patients
1	1 mg/kg	50mg	3-6
2	2 mg/kg	50mg	3-6
3	5 mg/kg	50mg	3-6
4	10 mg/kg	50mg	3-6

The following rules will be used at each dose level to determine whether or not to proceed to the next dose level:

- If 0 of 3 subjects at a given dose level experience a DLT (defined below), then escalation will proceed to the next dose level.
- If 2 or 3 of 3 subjects at a given dose level experience a DLT, then one of the following must occur:
 - If this happens at level 1, the study will be closed to further accrual and the regimen of pembrolizumab + BCG will be considered too toxic at any dose.
 - If this happens at level 2 or beyond, the previous level will be declared the maximum tolerated dose (MTD).
- If 1 of 3 subjects at a given dose level experiences a DLT, then an additional 3 slots will be added (for a total of 6 patients at that level):
 - If 1 of 6 total experiences a DLT, then escalation will proceed to the next level.
 - If ≥ 2 of 6 total experience a DLT, the previous level will be declared the MTD.

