16. Urine for sample (approximately 40-50 ml) for measurement of cytokines and cellular profiling by flow cytometry will be also be collected in a sterile cup throughout treatment, prior to dosing and an optional collection at the third void approximately 4-6 hours after each dose (weeks -2, 0, 1, 2, 3, 4, 5, 7, 9, 11, 13, 15, 17, 21, 25, 29, 33, 37, 41, 45, and 49). *NOTE: The first void will be 2 hours post-dosing as part of the treatment (may be used for PK sampling if participating in that component), the second void after dosing will not be used for any correlative studies and should be discarded. An optional urine for research will be obtained at the third void, which is typically 4-6 hours after dosing; however the time does not need to be exact and may be adjusted depending on patient needs/urgency.*

Urine will be collected in a sterile plastic container and transported to the Pathology Core Facility for processing. The cell pellets will then be sent to the Flow Cytometry lab for flow studies; the supernatant will be sent to Myriad Laboratories for cytokine analysis. See section 8.0 and the Lab Manual for additional details.

17. Archived tumor tissue for biomarker analysis and NGS is requested for all patients. A formalin fixed paraffin embedded tumor tissue sample (or newly obtained formalin fixed biopsy of a tumor lesion not previously irradiated) may be provided in the form of at least fifteen unstained slides (5 slides for IHC analysis and 10 slides for whole exome sequencing). A cytologic specimen will not be acceptable. In addition, if biopsies are performed during scheduled cystoscopies throughout the study, an additional 15 unstained slides from each will also be obtained for study purposes only if the samples contain tumor tissue. See section 8.0 and the Lab Manual for details.
18. Pembrolizumab will be administered intravesically at the assigned dose for the cohort at the following weeks: -2, 0, 2, 4, 7, 9, 11, 13, 15, 17, 21, 25 29, 33, 37, 41, 45 and 49.
19. BCG 50 mg will be administered intravesically during induction (6 weekly doses) and maintenance (weeks 7, 9, 11, 13, 15, 17, 21, 25 29, 33, 37, 41, 45 and 49); every effort should be made to administer doses on the same day each week, however a window of +/-2 days is permitted for each dose.

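### The half-dose BCG permission in 4.4 is counted from the last administration, so on the nominal calendar it has lapsed before any delayed maintenance dose (minor)

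*Combined protocol and SAP*

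**What the plan says.** Section 4.4 (Dose Delays/Modifications) covers Grade 2 local toxicity in pre-induction, induction and maintenance, and allows a delay of up to 14 days. For BCG it adds that "the dose should be delayed, and BCG may be re-challenged at half the dose (25mg"), and it leaves this to the treating physician's "discretion within 2 weeks (14 days) of the last administration". No separate window is given for maintenance.

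The discontinuation rule in the same paragraph counts from a different date: "If toxicity does not resolve to Grade 0-1 within 2 weeks (14 days) after scheduled dose, trial treatment should be discontinued".

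The maintenance calendar is in 4.1: "Intravesical BCG and intravesical pembrolizumab will be given every 2 weeks for the first 12 weeks of maintenance therapy" (weeks 7 to 17), "then every 4 weeks thereafter (weeks 21, 25, 29, 33, 37, 41, 45 and 49 for a total of 8 doses"). Table 4-1 and footnote 19 of Section 5 list the same weeks for BCG. Footnote 19 also sets the visit tolerance: "however a window of +/-2 days is permitted for each dose".

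Two other sections send the reader to 4.4 for BCG reductions. Section 4.2.1 rules out BCG escalation, "however the dose may be reduced based on toxicity criteria in section 4.4". Section 4.3 says "BCG may be reduced for toxicity as described in section 4.4".

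**The concern.** The half-dose sentence asks for a delay first and then sets a limit that starts at the previous instillation. With weekly dosing there is room for both. With maintenance spacing of 14 or 28 days, the limit is reached on or before the day the next dose is due, so any delay goes past it.

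At stake is whether the reduction promised in 4.2.1 and 4.3 can be used in maintenance, where 14 of the 20 BCG doses lie. After a maintenance delay, toxicity that has settled to Grade 1 or better allows treatment to resume at 50 mg, while the stated permission for 25 mg has run out. That is the wrong way round for a toxicity rule. Section 10.5 requires the study to follow the approved text exactly, so sites could reasonably disagree on whether a half dose on, say, day 30 is a deviation. Section 7.2.8 adds that BCG reactions tend to become more frequent and more severe as instillations accumulate, so the question can arise late in treatment.

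**Working it through.** **Inputs.** BCG weeks from 4.1, Table 4-1 and Section 5 footnote 19: 0-5, then 7, 9, 11, 13, 15, 17, then 21, 25, 29, 33, 37, 41, 45, 49. Permitted delay d = 1 to 14 days (4.4). Half-dose limit: day 14 after the last administration (4.4). Visit tolerance: 2 days either side (footnote 19).

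**Dose counts.** Weeks 7-17 give 6 doses and weeks 21-49 give 8, as 4.1 states. That makes 6 + 8 = 14 maintenance doses, and with 6 induction doses 20 in all.

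**Formula.** Let G be the spacing in days from the previous BCG dose. A dose delayed by d days falls on day G + d. It meets the half-dose limit if G + d ≤ 14, that is, if d ≤ 14 − G.

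| Doses | G | Delayed dose falls on | Largest d that fits | Delay days that fit |
|---|---|---|---|---|
| Weeks 1-5 (5 doses) | 7 | days 8-21 | 7 | 7 of 14 |
| Weeks 7-17 (6 doses) | 14 | days 15-28 | 0 | 0 of 14 |
| Weeks 21-49 (8 doses) | 28 | days 29-42 | −14 | 0 of 14 |

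The spacing for week 7 runs from week 5 (14 days) and that for week 21 from week 17 (28 days). Week 0 has no earlier BCG dose and is left out.

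**Effect of the visit window.** If the previous dose was given L days late and later visits are not moved, the delayed dose falls on day G − L + d.

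- Weeks 7-17: 14 − L + d ≤ 14 requires d ≤ L. With L = 1 or 2, a delay of 1 or 2 days fits, and nothing longer.
- Weeks 21-49: 28 − L + d ≤ 14 requires d ≤ L − 14. Even if the previous dose had itself been delayed the full 14 days, a one-day delay falls on day 28 − 14 + 1 = 15. No delayed dose fits.

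A previous dose delayed by more than 2 days would widen the first case under the same condition, d ≤ L. That is off the nominal calendar and assumes later visits stay where they were.

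**With the limit counted from the scheduled dose.** The condition becomes d ≤ 14, so all 14 delay days fit at every dose. The latest half dose would then fall on day 21 (weeks 1-5), day 28 (weeks 7-17) or day 42 (weeks 21-49) after the previous one. Those are the same latest days that the 14-day delay already allows for the full dose.

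**The case against.** The best defence is that 4.4 places BCG changes under standard of care, words the half dose as an option, and leaves it to the physician. A later sentence again allows reduction in line with standard of care, and a site might take the last administration to mean the last scheduled dose. Part of this stands: the text contains no express prohibition, so a reader who infers that a later half dose is forbidden goes further than the documents do. But the standard-of-care clause is spelled out by this very window, and the later sentence refers back to what was already described. The paragraph also uses the scheduled dose as its reference point elsewhere, so the two anchors are worded differently. If the sponsor intended the scheduled dose, the edit only says so.

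The second defence is that little depends on it. Section 7.2.8 reports that irritative symptoms usually last 24 to 72 hours and can usually be managed symptomatically, so few toxicity delays should be expected when doses are 28 days apart. It also reports no evidence that reducing the dose lessens irritative toxicity. This stands and limits the point to a modest clinical gain.

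Two stronger readings are tempting and are not supported:

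- **On-time doses.** A reader may note that at weeks 21-49 even an on-time half dose, on day 28, is past day 14, and count that as a further failure. The sentence is written for a dose that has been delayed. It does not address an undelayed one, so this is not a breach of the rule.
- **Number of patients.** A reader may want to apply the roughly 60% rate of bladder irritability in 7.2.8 to 24 patients. That figure has no stated grade and is not specific to maintenance. Twenty-four is a ceiling (4.1 gives a maximum of 18 evaluable), and treatment can end before or during maintenance. No count follows from the documents.

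**Conclusion.** The point holds as a wording error of minor severity. On the nominal calendar, none of the 14 maintenance BCG doses can be delayed for Grade 2 local toxicity and then given at 25 mg within the stated limit. Within the visit window the only exception is a delay of 1-2 days at weeks 7-17 after a previous dose that ran 1-2 days late. In induction, half of the permitted delay days fit. As written, this conflicts with the reductions that 4.2.1 and 4.3 promise and with the scheduled-dose anchor in the same paragraph.

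The conclusion rests on reading the last administration as the last dose actually given, and on taking the day-14 limit as the end of the written permission. The consequence is confined to maintenance dosing and how deviations are classified. It does not reach the primary objective: the DLT period covers pre-induction and the seven weeks of induction, and maintenance starts at week 7, so DLT and MTD decisions are essentially unaffected.

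Appendix C suggests how this arose, although that is history and not itself an error. The half-dose option came in with Amendment 2, with a rationale about induction. Amendment 7 later added maintenance BCG without listing 4.4 among the sections changed.

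**What to change.** In the half-dose sentence of 4.4, replace the time limit at the end of "discretion within 2 weeks (14 days) of the last administration" with *within 14 days after the scheduled dose*. This matches the discontinuation rule in the same paragraph and makes 25 mg available on any day on which 50 mg may already resume.

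The cost is one phrase. Visits, sample size, DLT definitions and the 14-day cap on delay stay as they are. There is no added exposure, because the half dose would be allowed only on days when the full dose already is.

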4.5.1 Immune-Related Adverse Events

The limited systemic absorption of chemotherapy agents and cytokines (i.e., IFN) when administered intravesically predicts that immune-related adverse events (irAEs) observed in patients receiving intravenous pembrolizumab will be rare. Nevertheless, all measures will be in place for careful monitoring and management should these occur

Table 4-4. Dose Modification and Toxicity Management Guidelines for Immune-related AEs Associated with Pembrolizumab

General instructions:				
Immune-related AEs	Toxicity grade or conditions (CTCAEv4.0)	Action taken to pembrolizumab	irAE management with corticosteroid and/or other therapies	Monitor and follow-up
Pneumonitis	Grade 2	Withhold	
 Administer corticosteroids (initial dose of 1-2 mg/kg prednisone or equivalent) followed by taper 	
 Monitor participants for signs and symptoms of pneumonitis Evaluate participants with suspected pneumonitis with radiographic imaging and initiate corticosteroid treatment Add prophylactic antibiotics for opportunistic infections
	Grade 3 or 4, or recurrent Grade 2	Permanently discontinue		
Diarrhea / Colitis	Grade 2 or 3	Withhold	
 Administer corticosteroids (initial dose of 1-2 mg/kg prednisone or equivalent) followed by taper 	
 Monitor participants for signs and symptoms of enterocolitis (i.e., diarrhea, abdominal pain, blood or mucus in stool with or without fever) and of bowel perforation (i.e., peritoneal signs and ileus). Participants with \geq Grade 2 diarrhea suspecting colitis should consider GI consultation and performing endoscopy to rule out colitis. Participants with diarrhea/colitis should be advised to drink liberal quantities of clear fluids. If sufficient oral fluid intake is not feasible, fluid and
	Grade 4	Permanently discontinue		

NU Study Number: NU 15U06
Merck Study Number: 3475-265

				electrolytes should be substituted via IV infusion.
AST / ALT elevation or Increased bilirubin	Grade 2	Withhold	
 Administer corticosteroids (initial dose of 0.5- 1 mg/kg prednisone or equivalent) followed by taper 	
 Monitor with liver function tests (consider weekly or more frequently until liver enzyme value returned to baseline or is stable)

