	Grade 3 or 4	Permanently discontinue	
 Administer corticosteroids (initial dose of 1-2 mg/kg prednisone or equivalent) followed by taper 	
Type 1 diabetes mellitus (T1DM) or Hyperglycemia	Newly onset T1DM or Grade 3 or 4 hyperglycemia associated with evidence of β -cell failure	Withhold	
 Initiate insulin replacement therapy for participants with T1DM Administer anti-hyperglycemic in participants with hyperglycemia 	
 Monitor participants for hyperglycemia or other signs and symptoms of diabetes.
Hypophysitis	Grade 2	Withhold	
 Administer corticosteroids and initiate hormonal replacements as clinically indicated. 	
 Monitor for signs and symptoms of hypophysitis (including hypopituitarism and adrenal insufficiency)
	Grade 3 or 4	Withhold or permanently discontinue ¹		
Hyperthyroidism	Grade 2	Continue	
 Treat with non-selective beta-blockers (e.g., propranolol) or thionamides as appropriate 	
 Monitor for signs and symptoms of thyroid disorders.
	Grade 3 or 4	Withhold or permanently discontinue ¹		
Hypothyroidism	Grade 2-4	Continue	
 Initiate thyroid replacement hormones (e.g., levothyroxine or liothyroinine) per standard of care 	
 Monitor for signs and symptoms of thyroid disorders.
Nephritis and Renal dysfunction	Grade 2	Withhold	
 Administer corticosteroids (prednisone 1-2 mg/kg or equivalent) followed by taper. 	
 Monitor changes of renal function
	Grade 3 or 4	Permanently discontinue		
Myocarditis	Grade 1 or 2	Withhold	
 Based on severity of AE administer corticosteroids 	
 Ensure adequate evaluation to confirm etiology and/or exclude other causes
	Grade 3 or 4	Permanently discontinue		
All other immune-related AEs	Intolerable/ persistent Grade 2	Withhold	
 Based on type and severity of AE administer corticosteroids 	
 Ensure adequate evaluation to confirm etiology and/or exclude other causes
	Grade 3	Withhold or discontinue based on the type of event. Events that		

		require discontinuation include and not limited to: Gullain-Barre Syndrome, encephalitis		

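### For immune-related adverse events, Section 4.4 lets pembrolizumab resume in five named entries where Table 4-4 ends treatment, and no visible text says which rule governs

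*Combined protocol and SAP*

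**What the plan says.** The third paragraph of Section 4.4 sets a general rule: "pembrolizumab will be withheld for drug-related Grade 4 hematologic toxicities, non-hematological toxicity", the latter at Grade 3 or higher with laboratory findings included, and also for severe or life-threatening events. It continues: "Delay by up to 2 weeks (14 days) is permitted. Treatment may resume when the toxicity resolves or improves to grade 1". If Grade 0-1 is not reached within 14 days after the scheduled dose, treatment is to be discontinued after consultation with the principal investigator and the DSMC. There is one exception, which needs the agreement of both: "subjects with a laboratory adverse event still at Grade 2 after 2 weeks may continue treatment in the trial only if asymptomatic and controlled". The paragraph neither excepts immune-related events nor refers to Table 4-4.

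Section 4.5.1 expects immune-related events to be rare by the intravesical route and adds: "Nevertheless, all measures will be in place for careful monitoring and management should these occur". Table 4-4 follows, titled "Dose Modification and Toxicity Management Guidelines for Immune-related AEs Associated with Pembrolizumab". Its rows include "AST / ALT elevation or Increased bilirubin" and "Nephritis and Renal dysfunction". For Grade 3 or 4 in both rows the action is "Permanently discontinue". The same action stands against Grade 3-4 myocarditis, Grade 3-4 pneumonitis and Grade 4 diarrhea/colitis.

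**The concern.** A Grade 3 or 4 immune-related event falls under both texts. Section 4.4 treats it as a reason to pause, with return allowed on recovery. Table 4-4 treats it as the end of pembrolizumab. Stopping complies with both; re-dosing complies only with Section 4.4.

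The laboratory exception is the sharpest case. An isolated Grade 3 transaminase rise that has fallen only to Grade 2 could be re-treated with the required agreement. Table 4-4 would have ended treatment at Grade 3, and it withholds even for Grade 2.

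What is at stake is the safety of an individual patient after a severe liver, kidney, heart, lung or bowel immune event, and consistent handling of such patients across dose cohorts.

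**Working it through.** The plan states no figure on this point, so the check compares the rules.

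**1. The two rules side by side.** Table 4-4 has nine named event rows. These are the entries with an unconditional permanent stop at Grade 3 or 4:

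| Immune-related event | Section 4.4, third paragraph | Table 4-4 |
|---|---|---|
| AST/ALT or bilirubin, Grade 3-4 | withhold; may resume at Grade 0-1, or at Grade 2 under the laboratory exception | permanent stop |
| Nephritis/renal dysfunction, Grade 3-4 | same, including the exception where the event is a laboratory one | permanent stop |
| Myocarditis, Grade 3-4 | withhold; may resume at Grade 0-1 | permanent stop |
| Pneumonitis, Grade 3-4 | withhold; may resume at Grade 0-1 | permanent stop |
| Diarrhea/colitis, Grade 4 | withhold; may resume at Grade 0-1 | permanent stop |

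That is five entries. Counted by grade, they are 2 + 2 + 2 + 2 + 1 = 9 event-by-grade combinations. The catch-all row for other immune-related events also ends treatment at Grade 4 or recurrent Grade 3. It is not in the count because it names no event.

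**2. Cases settled elsewhere.** Table 4-6 repeats the stop for Grade 3-4 pneumonitis, although Section 4.5.3 introduces that table only as a suggested plan. Setting pneumonitis aside leaves four entries, or 9 - 2 = 7 combinations. Table 4-3 requires permanent discontinuation for concurrent AST/ALT and bilirubin elevation beyond its stated multiples of normal. An isolated rise in one of them is not covered.

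**3. When the conflict can arise.** The resume-at-Grade-1 route is open only if recovery comes by 14 days after the scheduled dose. If onset is just after a dose, the longest time from onset is the interval to the next pembrolizumab dose plus 14 days:

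- 2-week intervals: 14 + 14 = 28 days
- week 4 to week 7: 21 + 14 = 35 days
- 4-week intervals, weeks 17 to 49: 28 + 14 = 42 days

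With later recovery, Section 4.4 also leads to discontinuation unless the laboratory exception is used.

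**4. Search for a ranking.** Section 4.5.2 opens by adding supportive care to the preceding table, which presupposes that Table 4-4 is applied. Its pointer back to Section 4.4 concerns only local bladder and urinary infections. For infusion-like reactions it says outright that the table is to be followed. The sentence before Table 4-7 makes that table residual to the other immune-related rules and does not mention Section 4.4. Sections 4.8 and 4.10 allow stopping for unacceptable toxicity but rank nothing.

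**5. The rules also differ the other way.** Table 4-4 continues pembrolizumab through Grade 3-4 hypothyroidism, and its note lets certain controlled endocrinopathies resume at Grade 2 or lower. Section 4.4 would withhold for Grade 3 and require Grade 1. Following the stricter text each time would therefore not reproduce Table 4-4.

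**The case against.** The strongest reply is that there is no practical conflict. Section 4.4 is permissive and Table 4-4 is directive, so an investigator who stops breaches neither. The table's title gives its scope as dose modification for exactly these events, and a specific rule ordinarily displaces a general one. Section 4.5.2 assumes the table is in use. Table 4-6 shows a sensible division of labour: the two-week limit bounds events that are withheld and does not reopen those that are stopped. The amendment history, cited only as background, records the table as the manufacturer's new dose-modification table, which supports an intent that it control. Any immune-related event of Grade 2 or higher must be discussed with the sponsor at once, and the laboratory exception needs two agreements and an asymptomatic, controlled patient.

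Most of this stands, and it limits the severity. It does not remove the point. The precedence remains an inference, and the safeguards bring in more people without saying which instruction they should apply. The ordinary resume-at-Grade-1 route states no DSMC consultation. Nor can Section 4.4 be set aside for immune-related events, because Table 4-4 shows almost no resumption criteria for the events it withholds.

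One caution concerns the absence itself. Table 4-4 begins with a general-instructions line under which nothing is legible in the available text. A ranking sentence may have stood there and been lost in conversion, so the claim is limited to visible text.

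**Conclusion.** Wrong as written: two safety rules in the same protocol give different instructions for the same immune-related events. The size is five entries of Table 4-4, one of them (pneumonitis) also stopped by Table 4-6, with concurrent transaminase and bilirubin elevation already settled by Table 4-3. Severity is minor to moderate. No MTD rule, DLT definition or sample-size figure is affected.

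A reader might infer more than the documents support:

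- That every severe hepatic, renal, cardiac or lung event is affected. Table 4-4 covers only immune-related events; other drug-related Grade 3 or higher toxicity properly stays under Section 4.4.
- That the protocol intends or directs rechallenge. Section 4.4 only permits it, and the natural reading is that the table prevails.
- That patients face a quantifiable excess risk. The documents give no rate for these events by this route, so no exposure estimate can be made.

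The conclusion assumes that no ranking was lost under the table's general-instructions line.

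**What to change.** Add a short statement to the third paragraph of Section 4.4 with three parts:

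1. For immune-related adverse events, the actions in Table 4-4 govern, with Table 4-6 for pneumonitis and Section 4.5.4.1 for confirmed Stevens-Johnson syndrome or toxic epidermal necrolysis.
2. Permanent-discontinuation entries override both the resume-at-Grade-1 rule and the Grade 2 laboratory exception.
3. The 14-day, Grade 0-1 resumption limit continues to apply to events that Table 4-4 only withholds, except where the table's endocrinopathy note says otherwise.

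The sponsor's clinical team should confirm that this is the intent and check what the general-instructions line of Table 4-4 contains. Aligning the Grade 3-4 row of Table 4-7 with the catch-all row of Table 4-4 is optional and not needed for this fix. The cost is amendment wording only, with no change to dose levels, DLT rules or sample size.
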